### **Frequency of Data Review**

All adverse events that are both serious and unexpected will be reported to the IRB, NIA PO, and the independent study monitor within 48 hours of the study's knowledge of the SAE. All adverse events will be reported as per the IRB's policies.

The PI and program manager will also report data on enrollment, data collection, adverse events, serious adverse events and unanticipated problems every quarter to the independent safety monitor.

The PI will report all adverse events and serious adverse events every 6 months to the program officer at the NIA. The PI and program manager will meet every week for the duration of the study.

Note that in the first month of the study, [name] and the project manager will review all adverse events/ serious adverse events with the independent safety monitor to ensure they agree with the determinations as to which ones are study related.

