**Lay Summary**

We propose a single-blinded, randomized-controlled, clinical trial to evaluate the impact of an innovative model of home-based palliative care on outcomes for patients with advanced dementia and their caregivers. 250 subjects (125 patients, 125 caregivers) will be enrolled from across the Mount Sinai Health System and randomized to receive the home-based palliative care program or usual care. Intervention patients will be cared for by a pyramid of palliative care focused providers, the core of which comprises specially trained community health workers, social workers, and registered nurses. These providers are supported by a palliative care advanced practice nurse and physician. All visits will be done by video or telephone from 3/19/20 due to the ongoing risk of transmission of COVID-19. Usual care patients will have the results of their baseline interview shared with their Mount Sinai provider. Additionally, caregivers in the usual care arm will receive training from a health coach on a health issue identified as important to them (e.g., smoking cessation, healthy eating). This is a kind of attention control. of this intervention on meaningful outcomes for patients, caregivers, and the health system. Outcomes are symptom control and quality of life in persons with dementia; caregiver burden; caregiver satisfaction with care; patient days in the hospital and ED visits. In exploratory analyses we will also determine if the intervention decreases costs of healthcare. Outcomes will be ascertained through interviews with caregivers, chart abstraction from the medical record, and the Mount Sinai Data Warehouse.

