#### **Primary and Secondary Study Endpoints**

1. Patient symptoms and quality of life (co-primary endpoints). Measured using Symptom Management at the End-of-Life in Dementia (SM-EOLD) and Quality of Life in Alzheimer's Disease (QOL-AD) respectively. Measured at baseline, 3 months, 6 months.
2. Caregiver burden, satisfaction with care, and depression. Measured using Zarit Burden Inventory, FAMCARE-10, and Patient Health Questionnaire 9 (PHQ-9) respectively. Measured at baseline, 3 months, 6 months. We will also study the effect of the intervention on caregiver self-efficacy, using the revised scale for caregiving self-efficacy.
3. Healthcare utilization: from the data warehouse as well as using the Resource Use Instrument (RUI) collected through interviews with patients. Healthcare cost: measured through the Mount Sinai Data Warehouse.

Study duration is 6 months.

**Protocol Was Already Approved** No  
by the Icahn School of Medicine at  
Mount Sinai (ISMMS) Institutional  
Review Board (IRB) Under a  
Different Principal Investigator

**Protocol Was Previously Submitted** No  
to an External(non-ISMMS) IRB

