**Feasibility of Meeting Recruitment Goals**

Our enrollment target is 4 dyads per month (50 dyads per year). Through preliminary analysis, we have identified around 1700 patients per quarter who have a diagnosis of dementia, and around 60% of these are in the advanced stages. To meet our enrollment target, we would have to enroll 5% of these patients. We are therefore confident of reaching our target.

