#### **1. Medications (patient subjects only)**

There are risks to patients related to the prescription of medications, particularly those that may be prescribed for pain (including opioids) and behavioral and psychiatric symptoms (antipsychotics). These medications will only be prescribed in accordance with clinical guidance, after careful consideration of the risks and benefits of their use. In particular, we will only use antipsychotics for the management of behavioral symptoms where reversible causes have been considered and treated as appropriate, and the patient is at extreme risk or in severe distress. In all cases where a new medication is commenced we will inform the patient's treating physician and counsel the caregiver about the medication.

Please note that we are enrolling patients with advanced dementia who are by definition at high risk of both worsening delirium and function, hospitalization, death and other serious events. As such these outcomes are expected and will not be considered SAEs.

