### **Provisions for Research Related Harm / Injury**

It is not anticipated that patients or caregivers will come to harm during this study, as the intervention does not differ substantially from routine clinical care that is based on clinical guidelines. The clinical team has vast experience and competence in managing side effects and adverse events related to medication use in these patients. Where adverse events related to medication use cannot be managed in the home, the patients will be admitted to hospital at Mount Sinai. Generally, this medical care will

be billed to the research subject and/or his/her health care insurance in the ordinary manner and the research subject will be responsible for all treatment costs not covered by insurance, including deductibles, co-payments and coinsurance. This does not prevent the research subject from seeking payment for injury related to malpractice or negligence. As outlined above, interviews can arouse emotions in patients and caregivers. We have outlined the provisions for this eventuality above.

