**Principal Monitor**

**Additional Monitors**

### **Specific Items That Will Be Monitored for Safety**

All SAEs, regardless of treatment group or relationship to research, will be reported to the IRB within 24 hours in a full written report. Note that these patients have advanced illness and are receiving palliative care. As such deaths will be recorded and regularly reported to the IRB but deaths are not in and of themselves considered SAEs due to the nature of the patient population. We will review each death and evaluate the relationship of that death to any medications prescribed or recommended by the study team. If the team believes there is a causal relationship between the prescription of the medication and the subject's death, this will be reported to the IRB as a serious adverse event.

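### The independent monitor's agreement on relatedness is tied to month 1, about 2 of 750 planned dyad-months, and a medication-related admission has no route to SAE status

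*Protocol*

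**What the plan says.** Protocol section 24, Frequency of Data Review, describes a joint review with the independent safety monitor. Its timing is "Note that in the first month of the study", and its content is that a study team member and the project manager "will review all adverse events/ serious adverse events with the independent safety monitor to ensure they agree with the determinations" on study-relatedness. The same section sets up continuing reports:

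- to the IRB, the NIA program officer and the monitor within 48 hours, for events that are both serious and unexpected;
- to the monitor every quarter, covering enrollment, data collection, adverse events, SAEs and unanticipated problems;
- to the NIA program officer every 6 months, covering adverse events and SAEs.

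None of these includes a later step at which the monitor agrees or disagrees with a relatedness call.

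On classification, section 10 (Medications) lists worsening delirium and function, hospitalization, death and other serious events, and concludes: "As such these outcomes are expected and will not be considered SAEs". Section 24 (Specific Items That Will Be Monitored for Safety) sends SAEs to the IRB within 24 hours and deaths to the IRB regularly. It has each death reviewed against medications that the study team prescribed or recommended. A death becomes an SAE on this condition: "If the team believes there is a causal relationship between the prescription of the medication" and the death. Section 10 (Provisions for Research Related Harm / Injury) foresees hospital admission in this case: "Where adverse events related to medication use cannot be managed in the home".

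**The concern.** Two things looked wrong.

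First, a review meant to align the monitor and the team on relatedness needs events to work on. The first month of a trial that enrolls slowly supplies few.

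Second, the rule that brings a medication-caused event back into the SAE class is written for deaths only. It also rests on the judgment of the team whose prescribing is in question. Section 10 itself names opioids and antipsychotics as sources of risk.

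At stake is how soon, and in what form, the independent monitor would see a pattern of deaths or medication-related admissions that differs between arms. The relatedness question cannot do this alone: it concerns medications from the study team, which control patients do not receive. Only a count by arm compares like with like. Section 24 plans no interim analysis. The SAP describes admissions by group under Utilization but does not mention deaths.

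**Working it through.** **Inputs.** 125 dyads (Lay Summary: "250 subjects (125 patients, 125 caregivers) will be enrolled from across the Mount Sinai Health System"). Six months per dyad (section 3: "Study duration is 6 months"). Accrual of 4 dyads a month, 50 a year (section 7, Feasibility). Enrollment over 2 years (section 9). The documents give no mortality, adverse event or dropout rate, so those below are assumptions.

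**1. The plan's own accrual figure.** 50 / 12 = 4.17 a month, which rounds to the stated 4 (4 × 12 = 48 against 50). At 50 a year, 125 dyads take 30 months rather than 2 years. Two years would need 125 / 24 = 5.21 a month, used here as the upper case.

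**2. Share of follow-up in month 1.** Planned total = 125 × 6 = 750 dyad-months. With even accrual, month 1 holds rate × 0.5. If everyone enrolls on day 1, it holds rate × 1.

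| Rate per month | Share of 125 dyads | Even accrual | All on day 1 |
|---|---|---|---|
| 4 | 3.2% | 2.0 / 750 = 0.27% | 4 / 750 = 0.53% |
| 5.21 | 4.2% | 2.6 / 750 = 0.35% | 5.21 / 750 = 0.69% |

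Losing 40% of dyads by 6 months at a constant rate (assumed) cuts the total to 125 × 6 × 0.4 / (−ln 0.6) = 587 dyad-months. The largest share is then 5.21 / 587 = 0.89%. With 1:1 allocation, about half of the 2 dyad-months, or 1, is in the intervention arm.

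**3. Events in that window.** For six-month mortality m, expected month-1 deaths = 2 × (−ln(1 − m) / 6).

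| Assumed m | Deaths in month 1 | Deaths over the trial (125 × m) | Chance of none in month 1 |
|---|---|---|---|
| 10% | 0.04 | 12.5 | 97% |
| 30% | 0.12 | 37.5 | 89% |
| 40% | 0.17 | 50 | 84% |

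The review covers all adverse events. At an assumed 0.1 to 1.0 events per patient-month it would see 0.2 to 2 events, against 75 to 750 over the trial.

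**4. Where each event goes, as written.**

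| Event | SAE? | IRB, 24 hours | Monitor, 48 hours | Quarterly monitor report |
|---|---|---|---|---|
| Death the team attributes to its medication | Yes by section 24, no by section 10 | Yes, under section 24 | Unclear: section 10 classes death as expected | Yes, as an SAE |
| Any other death | No | No; reported regularly | No | Not stated |
| Admission for a medication-related event | No; no exception given | No | No; classed as expected | Reportable as an adverse event; arm and relatedness call not required |
| Any other admission | No | No | No | Not stated |

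The third row is the gap. The exception in section 24 shows that the general rule was thought too broad for medication-caused deaths, yet nothing parallel covers admissions.

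**The case against.** The strongest reply is that independent oversight does not stop after month 1. The monitor gets quarterly adverse event reports, the IRB gets deaths, and the NIA program officer gets six-monthly reports. Section 10 also has the patient's physician informed of prescribing, and normally asked first. All of this stands. A reader might infer that an imbalance would stay hidden until the trial ends; the documents do not support that, because quarterly reporting does not depend on an interim analysis. What is missing is a required presentation by arm and a continuing agreement step.

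A reader might also infer that the SAE exclusion is what empties the month-1 review. It is not. That review covers all adverse events, and an event that is not an SAE can still be an adverse event. Only the short window empties it. Nor does the text keep deaths and admissions out of the quarterly report. It calls the medication problems that lead to admission adverse events, so those belong there. It simply does not ask for deaths and admissions to be listed as such.

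The month-1 step can fairly be read as early calibration rather than the main safeguard. That reading is reasonable, but calibration also needs cases.

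It can be said, too, that sections 10 and 24 do not strictly conflict over admissions: one passage classifies expected events, and another says where medication-related events are treated. Even so, an admission caused by medication falls under the exclusion as worded.

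Finally, section 24 names a separate data and safety monitoring plan, listed in section 26 as approved. It was not available for this review and may already settle the content of the monitor's report.

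**Conclusion.** The concern holds in limited form. The only step that these documents state for the monitor's agreement on relatedness covers about 2 of 750 dyad-months, and under 1% of follow-up in every scenario tried. That share rests on the protocol's accrual, sample size and follow-up; the expected event counts rest on assumed rates. Later monitoring continues, but the protocol does not require deaths and admissions to reach the monitor by arm with the team's call. The SAE rule has a specific gap: a medication-related admission misses both expedited routes, while a medication-related death has an exception. This should be corrected. It does not show that monitoring is absent. The part about the listing depends on what the separate monitoring plan says; the mismatch among the protocol's own sections would remain unless the protocol is aligned.

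**What to change.** 1. In section 24, Frequency of Data Review, keep the month-1 review, since it covers all adverse events. Add to the existing quarterly report a line listing and a count by arm of all deaths and hospital admissions, with the team's relatedness call, for the monitor to agree or query. Withhold it from the research coordinator who conducts the blinded follow-up interviews.
2. In section 24, Specific Items That Will Be Monitored for Safety, extend the causality review and the SAE exception from deaths to hospital admissions.
3. Reconcile the exclusion in section 10 (Medications) with section 24 and with the admissions foreseen under Provisions for Research Related Harm / Injury.
4. If the separate monitoring plan already requires the listing, align section 24 with it instead of adding a second rule.

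The cost is one table in a report already made and a little reading time for a monitor already in place, plus the team's causality review of admissions. Section 12 already has the chart abstracted after every hospitalization, and section 24 already has each death reviewed. Treatment, sample size and endpoints do not change.

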### **Rules for Alteration of Study Design**

This is a pilot randomized controlled trial and there are no provisions for alterations in study design.

### **Selection Procedures to Minimize Toxicity**

Not applicable.

### **Grading System to Evaluate Adverse Events**

We will consider adverse events according to the grading system to include: unanticipated events, adverse events, and serious adverse events.

### **Procedures to Assure Data Accuracy**

All data will be checked on a quarterly basis by the program manager to ensure the data is being entered with a high degree of accuracy.

### **Suspension Reported to**

If the study is suspended for any reason, we will report this to the IRB and the program officer at the NIA.

### **Anticipated Circumstances of Subject Withdrawal**

While we do not anticipate subjects wishing to withdraw, we do have procedures in place should subjects wish to withdraw and these are detailed in the consent form and will be emphasized by the research coordinator at the time of enrollment. Subjects will be withdrawn if they die, they transition to long term care, they have a hospital stay exceeding 30 days, or they relocate outside of Manhattan.

### **Primary or Secondary Safety Endpoints**

We are not performing any interim analyses.

Data Monitoring Committee Description	[name] - DSMP - Pall Care Home Dementia - R 56 - March 30 2020.pdf
DMC Charter Available	No
Will the Research Include Data Coordinating Center Activities?	No

**25. Funding**

**Funding Source Name** National Institutes Of Health/DHHS  

**Identify Substantive Differences Between Protocol and Funding Proposal**

---

**Funding Source Name** Fan Fox And Leslie R. Samuels Foundation  

**Identify Substantive Differences Between Protocol and Funding Proposal**

---

## **26. Attachments**

Type	Name	Version	Status	Filename	Uploaded Date
Consent Documents	Adult consent - with capacity.docx	1	approved	Adult with capacity COVID amended - clean 5.22.docx	05/22/2020
Funding Proposal / Grant Application	Completed Application Downlaoded 3 15 19.pdf	1	approved	Completed Application Downlaoded 3 15 19.pdf	06/02/2019
Other - Participant Educational Materials	Patient/caregiver letter for mailing	1	approved	Patient mailing letter_ng_clean.docx	03/06/2020
Consent Documents	Adult consent patient - lacking capacity.docx	1	approved	Adult without capacity 5.22 COVID_clean.docx	05/22/2020
Consent Documents	Adult consent caregiver.docx	1	approved	Caregiver consent clean 5.22 for COVID.docx	05/22/2020
Data Collection Sheet	Datasheet for data warehouse and screening.xlsx	1	approved	Datasheet for data warehouse and screening.xlsx	06/02/2019
Instruments	Study instruments.docx	1	approved	Study instruments.docx	06/02/2019
Consent - Phone Script	Telephone script - not consent - patient or LAR	1	approved	Telephone script_patient or LAR.docx	06/02/2019
Consent - Phone Script	Telephone script - not consent - caregiver	1	approved	Telephone script_caregiver.docx	06/02/2019
Funding Proposal / Grant Application	[name] - R56 for R01 AG067045-01.pdf	1	approved	[name] - R56 for R01 AG067045-01.pdf	03/06/2020
Other - Other IRB Correspondance	Comparative review form	1	approved	HRP-215 - FORM - 19-01975.doc	04/08/2020
Consent - Consent Document	Adult with capacity	1	approved	Adult with capacity CoC tracked.docx	04/10/2020
Data Monitoring Committee Description	[name] - DSMP - Pall Care Home Dementia - R 56 - March 30 2020.pdf	1	approved	[name] - DSMP - Pall Care Home Dementia - R 56 - March 30 2020.pdf	05/22/2020
Other - Other IRB Correspondance	Continuation form for study	1	approved	Continuing review 19-01975_v2.doc	05/28/2020

## Statistical Analysis Plan

ID: GCO 17-02787

Palliative Care at Home for Dementia

NCT03798327

[name] – PI

March 2020

**1. Overview.** For continuous outcomes, we will compare the changes from baseline across multiple repeated measurement points between different treatment groups using mixed linear model to control for within-subject effect.

**2. Descriptive Study.** We will characterize subjects with regard to baseline and follow-up measures and change between assessments. Descriptive statistics of demographics, disease-related and treatment related variables will be calculated and compared at baseline between the treatment group and control group. T-test, Chi-square, Fishers exact test will be used as appropriate.

**3. For the primary outcomes measures,** we will examine changes in outcomes over time. As possible, we will test the differences in mean total scores between the main predictors of treatment groups (intervention vs. control) and time (baseline, 3 months, and 6 months), and the interaction term between these two predictors, which indicates the variation of difference of outcome trajectories between interventions and controls by baseline scores.

**4. Utilization.** We will measure counts of utilization including, as applicable, those related to the number of hospital admissions, number of hospital days, number of days out of hospital, and ED usage. We will perform simple counts followed by descriptive statistics between the two groups.

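### SAP item 3 misdescribes its group-by-time interaction as variation by baseline score, and as written it does not use the collected baseline scores to adjust the treatment comparison

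*SAP*

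**What the plan says.** The Protocol (Section 3, Primary and Secondary Study Endpoints) names "Patient symptoms and quality of life (co-primary endpoints", scored by SM-EOLD and QOL-AD: "Measured at baseline, 3 months, 6 months". Both scores therefore exist before treatment starts. Allocation is 1:1 by dyad (Section 12), and "250 subjects (125 patients, 125 caregivers) will be enrolled" (Section 1, Lay Summary).

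SAP item 1 states the aim for continuous outcomes: "we will compare the changes from baseline across multiple repeated measurement points between different treatment groups using mixed linear model". SAP item 2 uses baseline values descriptively: "We will characterize subjects with regard to baseline and follow-up measures and change between assessments". SAP item 3, on the primary outcomes, says "we will examine changes in outcomes over time" and lists the model terms as "the main predictors of treatment groups (intervention vs. control) and time (baseline, 3 months, and 6 months", plus "the interaction term between these two predictors, which indicates the variation of difference of outcome trajectories between interventions and controls by baseline scores".

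The SAP lists no baseline-score covariate, no baseline-by-group term and no constraint that the arms share a baseline mean. Section 23 of the Protocol refers to a data analysis plan in an accompanying proposal, which is not among the documents.

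**The concern.** There are two separate problems.

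**Wording.** The closing words of the item 3 sentence describe effect modification, that is, a treatment effect that differs with the starting score. The listed terms cannot estimate that. This is the SAP's only explanation of the term that tests the co-primary endpoints. An analyst who took it literally could report the treatment effect as a baseline-dependent effect, or fit a different model.

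**Precision.** When baseline is an outcome level with a free mean in each arm, the estimate subtracts the chance baseline difference in full. Adjustment subtracts only the part that predicts the follow-up score. The planned estimate is valid under randomization but less precise than the same data allow. That matters with 125 dyads and with withdrawal for death, long-term care, long hospital stays and relocation (Protocol Sections 9 and 24).

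**Working it through.** **Inputs from the documents:** visits at baseline, 3 and 6 months; 125 dyads, 1:1, taken as 63 and 62; model terms group, time and group-by-time.

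**Inputs assumed:** ρ, the SDs, effect size, two-sided 0.05, dropout and compound symmetry. The documents give no power figure to reproduce. The SAP names no primary visit, so I use the 6-month contrast.

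**1. What the interaction estimates.** Write the mean in arm g (0 or 1) at visit t as μ + αg + β(t) + γ(t)g, with β = γ = 0 at baseline. Then

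γ(6) = [mean(1,6) − mean(1,0)] − [mean(0,6) − mean(0,0)],

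which is the between-arm difference in mean change. No individual baseline score appears in it. As a check, on one simulated complete data set the fitted interaction coefficient and the directly computed difference in mean change were both −0.05663547.

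**2. Variance with complete data and equal SDs (per patient, in SD² units).**

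- Planned (change): 2(1 − ρ)
- Baseline-adjusted: 1 − ρ²
- Ratio: (1 + ρ)/2, so the cut is (1 − ρ)/2

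| ρ | planned | adjusted | cut |
|---|---|---|---|
| 0.2 | 1.60 | 0.96 | 40% |
| 0.4 | 1.20 | 0.84 | 30% |
| 0.5 | 1.00 | 0.75 | 25% |
| 0.7 | 0.60 | 0.51 | 15% |
| 0.9 | 0.20 | 0.19 | 5% |

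Estimating a covariate costs a factor of about 1 + 1/(125 − 4), or 0.8%. The 5% at ρ = 0.9 then becomes about 4%.

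**3. Missing follow-up.** I used generalized least squares with monotone dropout, missing at random, half of the 6-month loss already present at 3 months, and all baseline scores kept. The cut in variance is:

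| missing at 6 months | ρ 0.4 | ρ 0.5 | ρ 0.7 |
|---|---|---|---|
| none | 30.0% | 25.0% | 15.0% |
| 20% | 25.7% | 21.3% | 12.6% |
| 30% | 23.3% | 19.2% | 11.3% |
| 35% | 22.1% | 18.2% | 10.6% |

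**4. Unequal SDs.** With k = SD at 6 months / SD at baseline and complete data, the cut is (1 − ρk)² / (k² + 1 − 2ρk). At ρ = 0.5 it is 43% for k = 0.8 and 11% for k = 1.25. Over ρ 0.2 to 0.9 and k 0.8 to 1.25, it runs from 0% (ρ = 0.8, k = 1.25, where ρk = 1) to 53% (ρ = 0.2, k = 0.8). It is never negative in large samples.

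**5. Illustrative power (normal approximation, ρ = 0.5, 0.5 SD effect).** With complete data the factor 1/63 + 1/62 is 0.0320. The planned variance is 1.00 × 0.0320 = 0.0320, and the adjusted variance is 0.75 × 0.0320 = 0.0240. Planned power is Φ(0.5/√0.0320 − 1.96) = Φ(0.835) = 79.8%. Adjusted power is Φ(0.5/√0.0240 − 1.96) = Φ(1.267) = 89.7%.

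| missing | planned | adjusted | dyads the planned model needs to match 125 adjusted |
|---|---|---|---|
| none | 79.8% | 89.7% | 125 × 0.0320/0.0240 ≈ 167 |
| 20% | 73.2% | 82.8% | 125 × 0.03763/0.02963 ≈ 159 |
| 30% | 68.8% | 77.8% | 125 × 0.04162/0.03362 ≈ 155 |

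Using the noncentral t lowers these powers by less than one percentage point. At ρ = 0.7 the gain is small: 95% to 97%, 91% to 94% and 88% to 91%. With a 0.3 SD effect at ρ = 0.5, power is 39% to 49%, 34% to 41% and 31% to 37%.

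**6. Simulation check.** REML fits with the correlation estimated (6,000 trials per cell, ρ = 0.5, true effect 0.5) gave these powers for the planned, common-baseline and covariate models: 79.4/89.3/89.1% complete, 73.2/82.6/82.2% with 20% missing, and 68.2/77.2/76.7% with 30% missing. All three were unbiased (mean estimates 0.500 to 0.503). Rejection under no effect was 4.3% to 5.2% throughout.

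**The case against.** The strongest reply has five parts.

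- **The slip is local.** The terms are listed and SAP item 1 states the aim as change from baseline, so a careful analyst would fit the right model. That is likely, but the sentence still contradicts the terms it explains.
- **The planned model is legitimate.** It is valid and unbiased, and I do not call it otherwise. Leaving out adjustment loses efficiency; it does not invalidate the test.
- **The unseen proposal may specify adjustment.** The phrase about baseline scores may be a garbled reference to it. This cannot be excluded. What can be said is that the SAP does not state any adjustment.
- **The size is conditional.** This stands. ρ, the SDs, the effect, dropout and the choice of the 6-month contrast are all assumed. The 5% to 40% range holds only for equal SDs and complete data. With 30% missing it is about 4% to 32%, and with unequal SDs the gain can vanish.
- **The Protocol calls the trial a pilot (Section 24, Rules for Alteration of Study Design).** True, but SAP item 3 still plans to test differences, and pilot status is no reason to prefer the less precise of two analyses of the same data.

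**Conclusion.** Both parts hold. The wording error needs no assumption: the listed interaction is the difference in change from baseline. The precision loss follows from the model as the SAP states it, with a size that depends on an unknown ρ: 15% to 30% of the 6-month variance for ρ 0.7 to 0.4 with equal SDs and complete data, and 11% to 23% with 30% missing at random. The gain shrinks towards zero as ρ approaches 1 under equal SDs. This should be fixed before analysis. It is a wording error plus an efficiency loss, not a bias, and adjustment does not address bias from death or withdrawal.

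**What to change.** 1. Choose one model for each co-primary endpoint and rewrite item 3 to match it.
   - **Option A:** keep baseline, 3 and 6 months as outcome levels and constrain the arm means to be equal at baseline. Replace the reference to baseline scores with: *the arm-by-visit terms are the baseline-adjusted between-arm differences at 3 and 6 months*.
   - **Option B:** model only the 3- and 6-month scores, with baseline score, baseline-by-visit, arm, visit, arm-by-visit and a within-patient covariance. Replace the phrase with: *the treatment effect is the adjusted arm difference at the named visit*. Do not call this change from baseline; in this model the arm-by-visit term alone is the 6-month effect minus the 3-month effect.
2. If the present unadjusted model is kept, replace the phrase with *in change from baseline*.
3. If a group main effect averaged over visits including baseline is kept, state that it is not the treatment test.

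The cost is SAP text and model specification only, with no new data, visits or patients. Option A has one parameter fewer per endpoint than the planned model. Option B spends two parameters on baseline and drops dyads with no follow-up score. Their power is nearly the same. If the proposal already specifies adjustment, carry that wording into the SAP.
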